6.4.2 Assumption Checks

For continuous outcomes, linearity will be assessed by plotting the conditional residuals from the models against the value of the linear predictor. No obvious trend should be evident (i.e., uniform horizontal band present). In the case we do not see a good fit, continuous outcome models will be fitted using alternative distributions.

For binary outcomes, if we do not have the needed sample (may run into convergence issues), then outcome will be analyzed using Fisher Exact.

For count outcomes, models will be fitted using either negative binomial or Poisson models. Choice of distribution will be based on dispersion and/or convergence issues.

Given the limited number of infants in some centers, if we run into convergence issues that cannot be resolved using standard statistical approaches, we will consider combining sites based on geographical locations. We will also consider reducing the number of covariates.

6.4.3 Covariates

All secondary regression models will include the stratification variable (site) as a random effect and will be adjusted for:

- Breastfeeding status
- Stabilization dose, continuous
- Maternal treatment which will be categorized as follow:
 - Methadone use
 - o Buprenorphine ± naloxone
 - Prescribed opioids other than methadone and buprenorphine ± naloxone
 - o None/Unknown

In case of mixing among the 4 groups the following rules will be followed:

- o If methadone is used with other opioid, classify as methadone
- If buprenorphine is used with other opioid, classify as Buprenorphine ± naloxone
- o If methadone is used with buprenorphine, classify based on which drug has been used most proximal to delivery.

Additionally, if the sample size allows, secondary analyses can be adjusted for critical covariates that are substantially imbalanced at baseline (both clinically and statistically significantly different)

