In contrast to variations for weaning in clinical practice, randomized trials have used 10% reductions of the stabilizing dose. In a single-site trial that compared methadone to morphine, clinical teams weaned both drugs by 10% reductions of the stabilizing dose with four-hour dosing intervals (15). The most recent, and largest (58 infants in each group), randomized clinical trial of NOWS treatment, performed by Davis et al., was a multi-center trial comparing methadone to morphine (18). In this trial, medical professionals weaned NOWS infants treated with methadone or morphine by 10% of the stabilization dose every 12 to 48 hours with cessation of drug therapy at 20% of the stabilization dose. Administration of methadone alternating with placebo every four hours and morphine every four hours facilitated blinding of nursery personnel to the opioid being used. The trial demonstrated that the length of treatment and hospital stay were shorter with methadone, compared to morphine, and these results may prompt a shift from morphine to methadone as the primary opioid to treat NOWS. There are no randomized trials to inform clinicians of potentially better regimens to wean morphine or methadone.

Common outcomes of clinical trials of NOWS treatment are length of treatment, length of hospital stay, and safety outcomes. Although clinically evident brain injury on a neurological exam is not anticipated among infants with NOWS, there is support for abnormalities of neurobehavior (24). Such information may be important to understand maternal well-being after hospital discharge of a NOWS-treated baby. This is an important domain of NOWS research, and there is a growing recognition that outcomes of NOWS investigations need to broaden to include measures beyond length of treatment and length of hospital stay (7).

The NNNS is a comprehensive evaluation of 12 domains of neurologic and behavioral functioning as well as signs of stress, administered by trained, certified examiners (25). The research community has used the NNNS to study multiple groups of high-risk infants, including those exposed to drugs *in utero* (opioids, cocaine) and prematurity (26). Among 1,248 mother-infant dyads enrolled in the Maternal Lifestyle Study, researchers performed NNNS assessments at one month *after* hospital discharge (27). Researchers identified five mutually exclusive neurobehavioral profiles from the 12 neurobehavioral

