APPENDIX 4. MORPHINE: EXAMPLE OF WEANING WITH DOSING EVERY THREE HOURS

For this and subsequent scenarios (**Appendices 5-7**), the difference in opioid dose between rapid and slow wean interventions is illustrated. Since there are no escalations, the intervention steps correspond to the dose levels listed in Table 4 (**Section 4.2.6**).

Scenario. 3.2 kg infant treated with morphine, stabilized on 0.06 mg/kg/dose, and undergoing either a rapid-wean or slow-wean intervention with medication administered at **three-hour intervals**.

Protocol. At the start of weaning, the morphine dose is decreased by 15% of the stabilization dose (rapid wean) or 10% of the stabilization dose (slow wean). The dose represents the actual mg administered.

Intervention Dose		Intervention Dose	
Level	Rapid Wean	Level	Slow Wean
Day of Randomization 100% of stabilization	0.19 mg q 3 h	Day of Randomization 100% of stabilization	0.19 mg q 3 h
Dose level A 85% of stabilization	0.16 mg q 3 h	Dose level A 90% of stabilization	0.17 mg q 3 h
Dose level B 70% of stabilization	0.13 mg q 3 h	Dose level B 80% of stabilization	0.15 mg q 3 h
Dose level C 55% of stabilization	0.11 mg q 3 h	Dose level C 70% of stabilization	0.13 mg q 3 h
Dose level D 40% of stabilization	0.08 mg q 3 h	Dose level D 60% of stabilization	0.11 mg q 3 h
Dose level E 25% of stabilization	0.05 mg q 3 h	Dose level E 50% of stabilization	0.10 mg q 3 h
Dose level F 0% of stabilization	Placebo	Dose level F 40% of stabilization	0.08 mg 3 h
Dose level G 0% of stabilization	Placebo	Dose level G 30% of stabilization	0.06 mg q 3 h
Dose level H 0% of stabilization	Placebo	Dose level H 20% of stabilization	0.04 mg q 3 h
	Observe off study drug		Observe off study drug
	Observe off study drug		Observe off study drug

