APPENDIX 7. METHADONE: EXAMPLE OF WEANING WITH DOSING EVERY 12 HOURS

Scenario: 3.2 kg infant treated with methadone, stabilized on 0.15 mg/kg/dose, and undergoing either a rapid or slow wean with medication administered at **12-hour intervals**.

Protocol: At the start of weaning, the methadone dose is decreased by 15% of the stabilization dose (rapid wean) or 10% of the stabilization dose (slow wean). The dose represents the actual mg administered.

Intervention Dose Level		Intervention Dose Level	
Rapid Wean		Slow Wean	
Day of Randomization 100% of stabilization	0.48 mg q 12 h	Day of Randomization 100% of stabilization	0.48 mg q 12 h
Dose level A 85% of stabilization	0.41 mg q 12 h	Dose level A 90% of stabilization	0.43 mg q 12 h
Dose level B 70% of stabilization	0.34 mg q 12 h	Dose level B 80% of stabilization	0.38 mg q 12 h
Dose level C 55% of stabilization	0.26 mg q 12 h	Dose level C 70% of stabilization	0.34 mg q 12 h
Dose level D 40% of stabilization	0.19 mg q 12 h	Dose level D 60% of stabilization	0.29 mg q 12 h
Dose level E 25% of stabilization	0.12 mg q 12 h	Dose level E 50% of stabilization	0.24 mg q 12 h
Dose level F 0% of stabilization	Placebo	Dose level F 40% of stabilization	0.19 mg q 12 h
Dose level G 0% of stabilization	Placebo	Dose level G 30% of stabilization	0.14 mg q 12 h
Dose level H 0% of stabilization	Placebo	Dose level H 20% of stabilization	0.10 mg q 12 h
	Observe off study drug		Observe off study drug
	Observe off study drug		Observe off study drug

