3.4 Sample Size

The projected effect size is a 2.0-day difference in the duration of opioid treatment between infants randomized to a rapid-wean intervention and infants randomized to a slow-wean intervention. The sample size was derived by using results from a recently completed trial comparing morphine-treated infants and methadone-treated infants in which the standard

deviation was 6.9 days for the morphine-treated infants and 8.0 days for methadone-treated infants (see protocol for more details). A standard deviation of 6.9 days was used to derive the sample size, anticipating that more infants will be treated with morphine. However, the primary analysis compares treatment regardless of drug used, and sample size was calculated irrespective of the proportion of infants treated with morphine or methadone.

The study will have two intervention arms (rapid-wean and slow-wean) with 251 morphine/methadone treated infants per intervention arm, for a total of 502 morphine/methadone treated infants. This will achieve 90% power to reject the null hypothesis with a significance level of 0.05 using a two-sided two-sample t-test. The null hypothesis will be morphine or methadone treated infants in both arms will have equal means when the population difference in the duration of opioid treatment is 2.0 days with a standard deviation of 6.9 days. Sample size recalculation was performed in July 2022, using a standard deviation of 6.2 based on data from enrolled infants up to June 2022. It was determined that a sample size of 404 is needed to reach 90% power to reject the null hypothesis with a significant level of 0.05 using a two-sided two-sample t-test, and 302 to reach 80% power. We chose this latter number as our target enrollment.

Subsequently, given continued enrollment challenges faced by this trial, the DSMC and NICHD decided to terminate the trial after December 31, 2023.

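### The SAP's pooled secondary models and sensitivity analysis 1 have no term for the infant's own opioid and fit one stabilization-dose slope, unit unstated, across morphine and methadone

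*SAP*

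**What the plan says.** SAP 4.1 fits the primary outcome (H1) with intervention as a fixed effect and site as a random effect, and nothing else. The pooled secondary models (SAP 4.1, 6.4.1, 6.4.3) add breastfeeding, maternal treatment and "Stabilization dose, continuous". Sensitivity analysis 1 (SAP 6.4.5) adds the same set to H1. In the model equation of SAP 6.4.1 dose has a single coefficient, and the methadone and buprenorphine indicators describe the mother's treatment, not the infant's. The infant's drug could enter a secondary model only through the clause in 6.4.3 on covariates found imbalanced at baseline.

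The infant's drug is an inclusion criterion (Protocol 4.1.1.2), is counted in the CONSORT diagram (SAP 6.4.1) and defines H2 and H3. Protocol 3.3.2 says of the earlier morphine-methadone trial that "the length of treatment and hospital stay were shorter with methadone, compared to morphine", and Protocol 3.3.4 gives dose escalation in that trial as 48% on morphine and 38% on methadone.

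The SAP states no unit for stabilization dose. Protocol 4.2.6 gives the calculator input per kg per day; the text of Appendix 8 gives it per kg per dose. Those two passages need to be reconciled in any case.

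**The concern.** A recorded baseline variable that predicts the outcome is normally worth including in a linear model even when the arms are balanced on it, because it removes residual variance. The imbalance clause does not supply this. Randomisation is stratified by hospital, so drug should be balanced, and the clause would then leave it out.

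The single dose slope adds a second difficulty. The protocol's worked examples include a "3.2 kg infant treated with morphine, stabilized on 0.06 mg/kg/dose" every three hours and a "3.2 kg infant treated with methadone, stabilized on 0.15 mg/kg/dose" every twelve. On that scale a high value may mean methadone or a long dosing interval, not severe withdrawal. With no drug term, one coefficient has to carry both meanings, and which way it leans depends on a unit the SAP does not name.

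At stake is the width of the confidence intervals for the pooled continuous outcomes. The target had already been cut to the 80%-power figure and the trial was then closed amid enrollment difficulties (SAP 3.4), so precision at no data cost has some value.

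**Working it through.** **1. The plan's sample sizes.** Inputs from SAP 3.4: "The projected effect size is a 2.0-day difference in the duration of opioid treatment", two-sided 0.05, SD 6.9, later re-estimated "using a standard deviation of 6.2 based on data from enrolled infants up to June 2022". Per arm, n = 2(z₀.₉₇₅ + z_power)² SD²/Δ².

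- SD 6.9, 90%: 2 × 10.507 × 47.61/4 = 250.1, so 251 per arm, 502 in total.
- SD 6.2, 90%: 2 × 10.507 × 38.44/4 = 201.9, so 202 per arm, 404 in total.
- SD 6.2, 80%: 2 × 7.849 × 38.44/4 = 150.9, so 151 per arm, 302 in total.

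All three match the SAP.

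**2. A drug term alone, ignoring site (upper bound).** The share of variance explained is R² = p(1−p)D²/SD². The methadone share p is 0.13 (chart review, Protocol 3.3.3) to 0.30 (planning figure, Protocol 5.2.3). The documents give no drug difference D in days. I assume 2, with a range of 1 to 4, because Protocol 5.2.3 calls the 2.0-day target similar to the morphine-methadone trial.

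- p = 0.30, D = 2: 0.21 × 4/38.44 = 2.2%.
- p = 0.13, D = 2: 0.1131 × 4/38.44 = 1.2%.
- p = 0.30, D = 1 and 4: 0.5% and 8.7%.

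At p = 0.30 and D = 2 the residual SD is 6.2 × √(1 − 0.0219) = 6.13. With 151 per arm, SE = 6.13 × √(2/151) = 0.706, and power = Φ(2/0.706 − 1.96) = 80.9%, against 80.0%. Required N falls from 302 to 296, from 404 to 396, and from 502 to 492. At D = 4, power at 302 infants is 83.5%.

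**3. With site as a random effect.** Simulation with 20 hospitals, N = 302 or 404, SD 6.2, 70% morphine, 400 trials per scenario. Adding drug to the SAP primary model cuts the SE by 0.4% (drug mostly set by hospital) to 1.1% (drug independent of hospital) at D = 2, and by 2.0% to 4.5% at D = 4.

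**4. Models that contain the dose slope.** The example doses in Protocol Appendices 4-7 reverse order with the unit:

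| Drug, interval | mg/kg/dose | doses per day | mg/kg/day |
|---|---|---|---|
| Morphine, 3 h | 0.06 | 8 | 0.48 |
| Morphine, 4 h | 0.08 | 6 | 0.48 |
| Methadone, 8 h | 0.10 | 3 | 0.30 |
| Methadone, 12 h | 0.15 | 2 | 0.30 |

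I used the same simulation, assuming a within-drug dose-outcome correlation of 0.3, dose CV of 30% and ICC of 0.05, and added drug and drug-specific slopes to the one-slope model:

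- Dose per dose: SE falls 3-5% at D = 2 and 5-9% at D = 4. A 3-5% cut is worth 1/0.97² = 1.06 to 1/0.95² = 1.11 times the sample.
- Dose per day: SE changes by about 0 to 0.6% at D = 2. At D = 4 it falls by 0.2-0.5%, or by up to about 3% if dose is unrelated to outcome.
- Once drug is in the model, separate slopes change the SE by no more than about 0.3%.

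**5. H5, total opioid.** At one day per level and no escalation, the slow arm receives 90+80+70+60+50+40+30+20 = 440% of a stabilization day, and the rapid arm 85+70+55+40+25 = 275%.

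- Morphine: 4.40 × 0.48 = 2.11 against 2.75 × 0.48 = 1.32 mg/kg, a difference of 0.79.
- Methadone: 4.40 × 0.30 = 1.32 against 2.75 × 0.30 = 0.83 mg/kg, a difference of 0.50.

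On these doses, drug changes both the level and the size of the arm effect. Simulated on assumed spreads, the SE for H5 falls by about 11-17% if dose is entered per dose and by about 0% if per day. Other assumed spreads move the first figure by a few points either way.

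**6. H4 and H6, binary.** The escalation rates of 48% and 38% give an odds ratio of (0.48/0.52)/(0.38/0.62) = 1.5 for drug. Simulating H4 at N = 302 with an assumed arm log odds ratio of 0.4, a drug term *raises* the SE of the arm log odds ratio by 0.6% (13% methadone) to 0.8% (30%).

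**The case against.** Much of the opposing case stands.

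- **Primary model.** A reader might infer that the main analysis forces one dose slope. It does not: the SAP primary model has no dose term. The protocol's own primary model (5.1.4) would force one.
- **Binary outcomes.** A reader might infer that the intervals for H4 and H6 are needlessly wide. Step 6 shows otherwise: in a logistic model a prognostic covariate shifts the conditional odds ratio and does not narrow its interval.
- **Site.** Opioid choice follows hospital practice (Protocol 4.2.6), so the site effect absorbs part of any drug difference. It does not absorb all of it, because hospitals may switch drug (SAP 3.2).
- **Evidence on drug.** The duration comparison in Protocol 3.3.2 comes from a trial whose figures cover the whole course of treatment (Protocol 5.2.4). This trial counts weaning only, with the same dose levels and timing rule for both drugs. A 2-day drug difference in weaning is therefore an assumption.
- **Dose scales.** Appendices 4-7 are labelled as examples. The calculator screens in Appendix 8 give 0.07/2.0 = 0.035 mg/kg/dose for morphine and 0.09/2.3 = 0.039 for methadone, nearly equal per dose, though 0.28 against 0.08 mg/kg/day.
- **Existing provision.** H2 and H3 fit each drug separately. Protocol 5.1.6 also plans a pooled Bayesian model with drug and drug-by-intervention terms, but SAP 6.5.1 does not carry it over.
- **Status.** SAP 6.4.4 treats everything beyond the primary as exploratory.

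What this leaves untouched is that the pooled continuous models use a dose covariate of unstated unit and omit a recorded baseline variable that the protocol itself links to outcome.

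**Conclusion.** The point holds as an efficiency matter for the pooled continuous outcomes: sensitivity analysis 1, H5 and H9. A reader might go further and infer bias in the arm effect. The documents do not support that, since drug precedes randomisation and allocation is within hospital.

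For days of treatment the loss is small: at most about 2% of variance and under 1 power point at an assumed 2-day drug difference, less with site in the model. Where one mg/kg/dose slope is fitted, the cost is about 3-5% in SE; with mg/kg/day it is close to nothing. H5 has the most to gain, but again only if dose is entered per dose. The drug difference, dose-outcome correlation, dose CV and ICC are assumptions, and the dose scales are the protocol's examples. This is a worthwhile refinement, and the planned conclusions do not depend on it.

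**What to change.** Before unblinding, or labelled post hoc for anything already analysed:

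1. Add primary opioid (morphine or methadone) as a fixed effect in the pooled continuous secondary models and in sensitivity analysis 1.
2. State the unit of the stabilization-dose covariate as mg/kg/day, or standardise dose within drug. This concerns the analysis variable only.
3. Report H5 by drug as well as pooled.

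Drug-specific dose slopes are optional, since they add little for duration once drug is in the model. It would also help to record why the protocol's Bayesian drug-interaction model was dropped, or to restore it.

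The cost is SAP wording and one or two extra parameters, with no new data. SAP 6.4.2 foresees convergence trouble from small centres and may reduce covariates; if so, the main effect of drug is the term to keep ahead of separate slopes.

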6.4.4 Subgroup Analysis

For the primary outcome the following subgroup analyses will be performed:

- 1. By race/ethnicity
- 2. By sex

Each model will be similar to the analysis described in section 6.4.1 but will also include fixed effect for the stratification variable as well as an interaction between intervention and the stratification variable. If

p-value for interaction is less than 0.10 then we will report the treatment effect within the specified subgroup. We will not correct for multiple testing as all analyses other than the primary are considered exploratory.

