 μ_i = expected value of outcome y_i

 β_0 = intercept, the expected mean number of treatment days when all covariates = 0

 β_1 = Intervention effect of fast vs slow wean interventions

 $\beta_2, \beta_3, \beta_4$ = effect of maternal treatment, compare to no treatment

 β_5 = effect of stabilization dose

 β_5 = effect of breastfeeding

 β_i = effect of the jth covariate added to the model

For normal outcomes, g(.) is the identity link function.

For binary outcomes, g(.) is the logit link function and we will assume that y_i follows Bernoulli distribution. Alternatively, we can follow Zou et al. (2003) and use the natural log function, and we will assume that y_i follows Poisson or negative binomial distribution. Decision will be based on manuscript writing team, if they prefer to report risks vs odd ratios.

For count outcomes, g(.) is the natural log function, and we will assume that y_i either follows Poisson or negative binomial distribution.

All hypothesis tests will be performed using a two-sided significance level of 0.05. Unless otherwise specified, results for each type regression performed will include the following:

- Normal regression
 - Unadjusted
 - Mean (and 95% confidence intervals (CI)) of the outcome in each treatment group.
 - Mean difference (and 95% CI) of the outcome between treatment groups.
 - Adjusted using pre-specified covariates.
 - Mean (and 95% CI) of the outcome in each treatment group.
 - Mean difference (and 95% CI and p-value) of the outcome between treatment groups.
- Logit Binomial regression
 - Unadjusted
 - Rate (and 95% CI) of the outcome in each treatment group
 - Odds Ratios (and 95% CI) of the outcome between treatment groups
 - Adjusted using pre-specified covariates.
 - Rate (and 95% CI) of the outcome in each treatment group
 - Odds Ratios (and 95% CI and p-value) of the outcome between treatment groups.
- Log-Binomial or Poisson regression
 - Unadjusted
 - Risk (and 95% CI) of the outcome in each treatment group
 - Relative risk (and 95% CI and p-value) of the outcome between treatment groups
 - Adjusted using pre-specified covariates.
 - Risk (and 95% CI) of the outcome in each treatment group
 - Relative risk (and 95% CI and p-value) of the outcome between treatment groups.
- Poisson or negative binomial regression
 - Unadjusted
 - Rate (and 95% CI) of the outcome in each treatment group
 - Relative rate (and 95% CI and p-value) of the outcome between treatment groups

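### SAP 6.4.4 commits to sex and race/ethnicity effects only when the interaction p-value is below 0.10, a gate that inflates reported heterogeneity on average

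*SAP*

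**What the plan says.** SAP 6.4.4 opens with "For the primary outcome the following subgroup analyses will be performed" and lists two variables, race/ethnicity and sex. Each model adds the subgroup variable and its interaction with the intervention. If the "p-value for interaction is less than 0.10 then we will report the treatment effect within the specified subgroup". The section closes with "We will not correct for multiple testing as all analyses other than the primary are considered exploratory".

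Three other places bear on whether the effects would be reported anyway:

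- **SAP 6.4.1** sets default outputs (group means and mean differences with 95% CIs), introduced by "Unless otherwise specified, results for each type regression performed will include the following". Section 6.4.4 does specify otherwise, and the default list is by treatment group, not by arm within subgroup.
- **SAP 6.8** lists potential displays. None is a subgroup table. It adds only that further tables of model results are possible.
- **Protocol 5.1.6** treats the morphine and methadone subgroups differently. Estimates and 95% credible intervals are to be given for each, together with the probability that the subgroups differ, and no p-value condition applies. The drug-specific comparisons in the SAP (H2 and H3) are also ungated.

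**The concern.** When an estimate is shown only if its own test crosses a threshold, the estimates that are shown are a selected set. Here the selection acts on the estimated interaction, so the sex or race/ethnicity differences that reach the report are too large on average.

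The complementary problem is what the reader is not assured of seeing. If the interaction p-value is 0.10 or above, the plan promises no subgroup estimate and no interval. A reader could not then tell whether the effect looked similar in boys and girls or whether the data were too thin to say. With a trial sized for 80% power on the overall effect and then closed because of slow enrollment, the second possibility is a live one.

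**Working it through.** **Inputs**

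- Overall effect: "The projected effect size is a 2.0-day difference in the duration of opioid treatment" (SAP 3.4).
- SD: 6.2 days, from the July 2022 recalculation, "using a standard deviation of 6.2 based on data from enrolled infants up to June 2022". The original value was 6.9: "A standard deviation of 6.9 days was used to derive the sample size".
- Number of infants: 302, the revised target in SAP 3.4. The final number is not stated, so 150 is used as an assumed low case.
- Sex split: 51.7% male, from the chart review of exposed infants in protocol Appendix 1. This is an assumption for the trial.
- Race split: 74% white against all others, from the same table. This too is an assumption, and it reduces race/ethnicity to two levels.
- Gate: interaction p < 0.10, two-sided, so |z| > 1.645.
- True interaction: not given anywhere. The assumed range is 0, 1, 2 and 4 days.

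**Reproducing the plan's own figures**

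Infants per arm = 2 × (z for alpha + z for power)² × SD² / 2.0².

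- 80% power, SD 6.2: 2 × 7.849 × 38.44 / 4 = 150.9, so 151 per arm and 302 in total.
- 90% power, SD 6.2: 2 × 10.507 × 38.44 / 4 = 201.9, so 202 per arm and 404 in total.
- 90% power, SD 6.9: 2 × 10.507 × 47.61 / 4 = 250.1, so 251 per arm and 502 in total.

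All three match the SAP. The documents give no figure for the subgroup gate itself.

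**The gate**

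With arms balanced within subgroups of size n1 and n2, SE(interaction) = SD × sqrt(4/n1 + 4/n2).

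Sex, 302 infants: n1 = 0.517 × 302 = 156.1 and n2 = 145.9.
SE = 6.2 × sqrt(0.0256 + 0.0274) = 1.43 days.
Threshold = 1.645 × 1.43 = 2.35 days, which is more than the whole 2.0-day planned effect.

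| Case | SE (days) | Smallest estimate that passes (days) |
|---|---|---|
| Sex, 302 infants | 1.43 | 2.35 |
| Race 74/26, 302 infants | 1.63 | 2.68 |
| Sex, 150 infants | 2.03 | 3.33 |
| Race 74/26, 150 infants | 2.31 | 3.80 |

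**What passes, and at what size (sex, 302 infants, SD 6.2)**

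The estimate is taken as normal around the true interaction with SE 1.43. The chance of passing is the probability of lying beyond ±2.35. The mean size is the average absolute estimate given that it passes.

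| True interaction (days) | Chance of passing | Mean absolute size if reported (days) | Ratio to truth |
|---|---|---|---|
| 0 | 10% | 2.9 | – |
| 1 | 18% | 3.1 | 3.1 |
| 2 | 40% | 3.4 | 1.7 |
| 4 | 88% | 4.3 | 1.08 |

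In the 4-day case about 43% of the reported estimates fall below the true value.

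At 150 infants, a true 2-day interaction passes 26% of the time (sex) or 22% (race), with mean reported sizes of 4.5 and 5.1 days.

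With no true heterogeneity, the chance that at least one of the two tests passes is 1 − 0.9² = 19%, if they are independent.

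**Without the gate**

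At 302 infants the interaction would carry a 95% half-width of 1.96 × 1.43 = 2.8 days. Each sex-specific effect would carry one of about 2.0 days: 1.96 × 6.2 × sqrt(4/156.1) = 1.95 and 1.96 × 6.2 × sqrt(4/145.9) = 2.01. These intervals are wide, but the estimates are not selected.

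**The case against.** The sentence in 6.4.4 is a one-way commitment. It says what happens when the p-value is below 0.10 and is silent about the rest. It does not say that the interaction estimate or its p-value will be withheld, and the display list in 6.8 leaves room for further tables. A reader might infer that consistent subgroups will never be shown. The text does not support that. What stands is narrower: the plan promises the subgroup effects only below the threshold, and a threshold has little purpose unless it governs reporting.

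A reader might also infer that only exaggerated differences can appear. That is too strong. A true 4-day interaction would usually pass with little average inflation, and would often be reported below its true size.

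The ratio of about three describes the interaction at an assumed true value of 1 day. The gated quantity is the effect within each subgroup, which moves less. With equal subgroups and an overall effect of 2 days, the larger subgroup effect goes from 2 + 0.5 = 2.5 days to 2 + 1.55 = 3.55 days, about 1.4-fold.

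The absence of multiplicity correction is not a separate fault, because the section states it openly and calls these analyses exploratory. That label does not answer the selection problem, however. Exploratory estimates are most useful when all of them are shown with their uncertainty.

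**Conclusion.** The point holds as a modest reporting fault. SAP 6.4.4 ties the sex and race/ethnicity effects to an interaction p-value below 0.10, and nothing else in either document commits to reporting them otherwise. Followed as written, the rule inflates reported heterogeneity on average. At the target size, a true sex interaction smaller than about 2.35 days can pass in the right direction only as an overestimate.

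The figures rest on assumptions: 302 infants (the trial may have closed with fewer), an SD of 6.2 days, a near-equal sex split taken from a chart review, balanced arms within subgroups, and no allowance for site effects or the truncation at 35 days. The race figures also assume two levels. With more levels, the test has more than one degree of freedom and the day thresholds do not carry over.

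The primary analysis, the drug-specific comparisons and the safety analyses are untouched.

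**What to change.** In SAP 6.4.4, delete the condition that subgroup effects are reported when the interaction p-value is below 0.10. Replace it with a commitment to report, for sex and for race/ethnicity, the interaction estimate with its 95% CI and p-value, and the treatment effect with its 95% CI in every pre-specified subgroup, whatever the p-value and labelled exploratory. Add the table or forest plot to the list in 6.8.

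The interaction models are already planned, so no new data or analysis is needed. The cost is one extra display. It would also bring these subgroups into line with the ungated reporting that protocol 5.1.6 sets for morphine and methadone.
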